# **1. Introduction**

Atrial fibrillation (AF) is the most prevalent type of arrhythmia within an adult population and is characterised by disorganised, chaotic, electrical activity and thus ineffective atrial contraction causing irregular ventricular contraction (Wyndham, 2000). AF can be categorised into three different groups: paroxysmal, persistent, and permanent. The prevalence of AF increases with age and is associated with, but not limited to, a range of risk factors including hypertension, obesity, and alcohol consumption (Staerk, *et al.*, 2017). There is a plethora of both cardiac and non-cardiac causes of AF and the cause is not always clear for each patient. Furthermore, causes of AF can also present as the by-product of AF, this increases the difficulty in determining the individual patient's cause of onset. A diagnosis of AF can be incidental as not all patients are symptomatic. If AF goes undetected, this puts the patient at an increased risk of blood clot formation and stroke (Markides and Schilling, 2003).

Patients suspected of having AF are routinely referred for a transthoracic echocardiogram (TTE). It is common for AF patients to have a dilated left atrium (LA) and this can be visually confirmed in addition to the LA area and volume measurements (Van De Vegte, et al., 2021). However, as LA measurements are limited to area and volume size, LA strain measurements may be taken but these are not routinely performed during standard TTEs. LA strain is measured using a type of speckle-tracking echocardiography (STE) technique which focuses on the subtle longitudinal changes within the myocardium to analyse myocardial deformation (Gan, et al., 2018). Strain imaging of the LA produces three functional strain values (contractile, conduit and reservoir) which correspond to different stages of the cardiac cycle (Jarasunas, et al., 2018). As patients in AF lack normal atrial contraction and have a loss of atrial kick, it is expected that the contractile strain, associated with LA contraction, is not present. However, the conduit and reservoir functions can still be compared across all three study groups to create a scale to suggest and predict whether a patient is likely to develop AF in the future; prior to any changes in LA size. Furthermore, this can then be further compared to determine whether there are any significant differences in strain patterns between the different groups of AF.

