# **1.2 Research Question**

Can measurements of left atrial strain, along with correlating changes in left atrium area and volume size, be used as an early predictor of atrial fibrillation?

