#### 2.2 Method

Patient selection:

Potential candidates for this study will have been referred for a TTE by a healthcare professional. The referrals will be reviewed and if the patient meets the initial eligibility criteria, they will be considered as part of this study. The initial eligibility criteria consist of being over the age of 50 (although patients will be age-matched across the three groups) and falling within the control (normal sinus rhythm), disease-control (controlled hypertension) or disease groups (chronic AF).

Data collection:

The images obtained from the TTE scan will be stored on the ultrasound machine as well as the picture archiving systems (PACS) on the computer. The measurements to be compared are:

- Left atrium area
- Left atrium volume
- Left atrium strain measurement and analysis using the R wave

The first two measurements are routinely performed during TTEs, but atrial strain measurements are not routinely performed. This additional measurement will not affect or delay the TTE results and report from being sent back to the referrer or delay any further correspondences with other healthcare professionals. Atrial strain measurements will be conducted using the AFI LA atrial strain tool provided by GE Healthcare. These three measurements will be compared across the three groups and tested for a statistically significant difference. Providing that there is a significant

difference, particularly between the control and disease groups, a subsequent comparison will be conducted between the three groups of AF using the existing data.

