#### 2.2.1 Study Type

Single centre case-control study, quantitative and a prospective study.

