#### 2.2.2 Study Overview

- Study design quantitative, observational, case-control study.
- Patients will be assigned to one of three groups: control group (normal sinus rhythm), disease-control group (controlled hypertension) and disease group (chronic atrial fibrillation).
- Patients will be required to visit the department on one occasion. This will be as part of either a routine or urgent referral for a transthoracic echocardiogram (TTE).
- TTEs are stored on both the ultrasound machines and computer picture archiving systems (PACS). Measurements can be taken on either the ultrasound machine or on the PACS following the patient's scan. The data obtained from these scans that will be utilised include patient demographics, heart rate and rhythm, LA area and volume measurements as well as LA strain measurements. This will be pseudo-anonymised using two Excel spreadsheets and the document will be password encrypted on a NHS OneDrive account
- Study site: within the Cardio-Respiratory department at Withybush General Hospital, there are five sonographers. This creates a throughput of approximately 60 TTE scans per week. With an expected data collection period of five months, this would equate to approximately 1200 outpatient scans factoring in annual leave and sickness. Additionally, inpatient scans can boost this number, but is dependent on current demand.

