#### Inclusion criteria:

- Criterion 1: subjects will be included in the study if they are within one of the following groups:
  - Known to be in normal sinus rhythm, are normotensive and have no underlying health problems.
  - Known to be in normal sinus rhythm and have controlled hypertension. This must have been diagnosed by a healthcare professional and the patient should be taking appropriate antihypertensive medication.
  - Known to have chronic atrial fibrillation (persistent or permanent AF). This must have been diagnosed by a healthcare professional and the patient should be appropriately anticoagulated.
- Criterion 2: subjects should ideally be ≥ 50 years, but subjects will be age matched across all three groups.
- Criterion 3: patients should have an EF  $\ge$  50%.
- Criterion 4: good quality TTE images.
- Criterion 5: No valvular pathologies.
  - Patients with AF that have < moderate valvular pathologies may be considered (as per the British Society of Echocardiography Guidelines).

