#### 2.2.6 Statistical Analysis Plan

Continuous data normality will be assessed utilising the Shapiro-Wilk test. Nonparametric data will be analysed via Mann-Whitney U tests and Kruskal-Wallis oneway ANOVA tests. If data shows a normal distribution, to compare the LA strain values between the control (NSR) and disease (AF) groups an independent T-test can be performed; this will establish whether there is an initial statistically significant difference between the two. Following this, to compare the mean strain values for each phase between the three groups, a one-way ANOVA must be performed. A one-way ANOVA can also be performed to determine any significant differences between the strain values between AF groups. These data analysis methods will also be repeated to analyse LA area and volume. To assess whether LA area and volume size correlate with LA strain, a Pearson correlation coefficient must also be performed. Furthermore, to determine whether LA strain may be used as an early predictor of AF, linear regression models must be adapted. For categorical data, such as gender, chisquared tests will be performed to determine any significant difference between groups. All statistical tests will be performed using the Prism GraphPad software.

It is expected that there will be a significant difference in strain values between NSR and AF participants. It is also expected that an increase in LA area and volume size will correlate with a decrease in LA strain values.

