### 2.4 Timescale

The project completion date is estimated to be March 2024 with the possibility of publishing following this. An overview of the entire project timescale can be visualised in the Gantt Chart – *see Appendix Figure 3*. The project has been split into three phases: project planning, data collection and analysis and dissertation write up and submission. The planning stage includes sponsorship and ethics approval and has an estimated completion date of May 2023. Following this, data collection and analysis may commence and in order to allow for sufficient data collection, a deadline of the end of November 2023 has been set. Furthermore, the end of January 2024 has been set to complete data analysis. The final stage consists of the write up of results, discussion and conclusion. Some of which may commence alongside data analysis and should be complete at the end of February 2024, ready for March submission. The date of the last visit for the patient will denote the end of the study. There are no follow-ups post echocardiogram required for this study, only data collection and analysis after this point.

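### Section 2.2.6 uses linear regression to decide whether LA strain predicts AF early, but a one-visit study of already diagnosed AF observes no new AF, so no model can support that conclusion

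*Combined protocol and SAP*

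**What the plan says.** Section 1.2 asks whether LA strain, with changes in LA size, can "be used as an early predictor of atrial fibrillation". The Introduction gives the intended meaning: the strain comparison should let the investigators "create a scale to suggest and predict whether a patient is likely to develop AF in the future; prior to any changes in LA size". The Study Summary says much the same.

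Section 2.2.6 gives the prediction part of this question one analysis: "to determine whether LA strain may be used as an early predictor of AF, linear regression models must be adapted". It names no dependent variable, covariates or performance measure. The Pearson correlation in that section covers the LA-size part.

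The design is set out as follows:

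- Section 2.2.1: "Single centre case-control study, quantitative and a prospective study".
- Section 2.2.2: "Patients will be required to visit the department on one occasion".
- Section 2.2.4, inclusion criteria for the disease group: "Known to have chronic atrial fibrillation (persistent or permanent AF). This must have been diagnosed by a healthcare professional".
- Section 2.4: "There are no follow-ups post echocardiogram required for this study, only data collection and analysis after this point".
- Section 2.2: groups are formed by current status, "although patients will be age-matched across the three groups".

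Paroxysmal AF may be included, but only for the comparison between AF types.

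**The concern.** To show that a marker predicts a disease early, the marker must be measured before the disease starts. Here it is measured afterwards in every case, and nobody in sinus rhythm is followed to see who develops AF. No section plans record linkage or later ascertainment, so the word prospective in section 2.2.1 can describe only how the data are collected.

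The protocol itself recognises the rival explanation. The Lay Summary says that electrical and structural changes can result from AF as well as cause it, and the Introduction says the same of LA enlargement. If AF lowers strain, the AF group will have low strain even if strain was normal beforehand.

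As written, a small p-value from the regression would be read as support for an early predictor. Sections 1.1, 2.3 and 4.1 link that claim to monitoring and medication, and section 4.1 presents it as a potential benefit to participants.

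**Working it through.** **1. The plan's own figure.** Section 2.2.5 gives a difference of 4.0, SD 7.5, alpha 0.05, power 0.85 and three groups. With equally spaced means 0, 2 and 4, f = √(8/3)/7.5 = 0.2177. With N = 234, λ = 234 × 0.2177² = 11.093, the critical F on 2 and 231 df is 3.035, and power is 0.851. This matches the G*Power output in the Appendix. The sample size therefore stands, but it covers a cross-sectional difference in means and nothing else.

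**2. New AF events.** The sinus-rhythm groups hold 2 × 78 = 156 people. The expected number of new cases is 156 × (1 − exp(−rate × follow-up)). With follow-up of 0 this is 0 at any rate.

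**3. Two explanations, one dataset.** Take d = 4.0/7.5 = 0.533 and 78 AF cases against 78 controls.

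- A: strain is already low before AF, and AF does not change it.
- B: strain is normal before AF, and AF lowers it.

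Both imply the same distributions at the single visit. In 4,000 simulated studies of each:

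| | A | B |
|---|---|---|
| Share of studies with p < 0.05 | 0.911 | 0.915 |
| AUC at the visit | 0.647 | 0.647 |
| AUC of pre-onset strain for future AF | 0.647 | 0.500 |

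In general, the AUC at the visit is Φ(d/√2). If AF itself causes a share s of the difference, the AUC for future AF is Φ(d(1 − s)/√2). At d = 0.533 and s = 0.25, 0.5, 0.75 and 1, this is 0.611, 0.575, 0.538 and 0.500. The study cannot estimate s. A larger difference does not help (d of 1.0 and 1.5 are assumed):

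| d | AUC at the visit (95% CI, 78 vs 78) | AUC for future AF, s from 1 to 0 |
|---|---|---|
| 0.533 | 0.647 (0.561 to 0.733) | 0.500 to 0.647 |
| 1.0 | 0.760 (0.685 to 0.835) | 0.500 to 0.760 |
| 1.5 | 0.856 (0.796 to 0.916) | 0.500 to 0.856 |

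**4. What the linear model would add.** Suppose AF status is the outcome and strain the only predictor. The p-value is then that of the NSR-AF t-test already planned; the largest gap across the simulated studies was 9 × 10⁻¹⁶. The mean fitted probability of AF is fixed by sampling at 78/156 = 0.50, or 78/234 = 0.33 with all three groups, whatever the true incidence. If strain is the outcome instead, the model does not address prediction.

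**5. Age, the matching factor.** Suppose age has the same distribution in both groups and correlates r with strain within groups. The log odds ratio per strain point is D/SD² = 4.0/56.25 = 0.071 without age and D/(SD²(1 − r²)) with age. For assumed r = 0.2, 0.3, 0.4 and 0.5, the latter is 0.074, 0.078, 0.085 and 0.095. Leaving age out thus shrinks the log odds ratio by r²: 4%, 9%, 16% and 25%.

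**The case against.** The strongest reply is that little depends on the regression sentence. The hypotheses in section 2.1, the power calculation and the first key outcome in section 2.3 are all cross-sectional. Some of the wording is tentative, and the protocol acknowledges that cause and effect may run either way. This is true, and those analyses are left alone. But section 1.2 makes early prediction the research question, and section 2.2.6 says the regression is there to determine it. The statements in sections 1.1 and 2.3 that monitoring will follow are not hedged.

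A second reply concerns the figures. Scenarios A and B agree by construction, so the simulation illustrates the point and does not prove it. It uses contractile strain inputs, although the Introduction expects contractile strain to be absent in AF, and it leaves out the hypertension group. All of this stands. The conclusion rests on step 2, which needs no simulation. A third group in sinus rhythm, also not followed, supplies no time order either.

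Third, the t-test equivalence holds only for one predictor, two groups and a pooled variance. The fixed mean probability applies equally to ordinary logistic regression, and the age attenuation depends on assumed correlations. These limits are correct. They concern the choice of model, which is secondary to the missing time order.

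**Conclusion.** The concern holds and must be fixed. The study can show whether strain differs between people with and without diagnosed AF, and how well it separates them. It cannot show that low strain comes before AF: it observes 0 new AF events, and all 78 planned cases are measured after diagnosis. This follows from the design and needs no assumed value. At the plan's inputs, a cross-sectional AUC of 0.65 is compatible with anything from 0.50 to 0.65 for future AF, if AF accounts for between all and none of the difference. Replacing linear with logistic regression corrects the model form but not the conclusion, so both must change.

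**What to change.** **Section 2.2.6.** Replace the linear-regression sentence with text such as:

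> Discrimination of already diagnosed persistent or permanent AF (78) from NSR controls (78) will be assessed by logistic regression on one LA strain measure (reservoir or conduit), named before any strain data are analysed, with age, the matching factor, in the model. If participants are matched individually, conditional logistic regression on the matched sets will be used. The odds ratio per strain point and the AUC of strain will be reported with 95% CIs. AF versus controlled hypertension (78) will be reported separately. These analyses do not estimate the risk of future AF.

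The Introduction says that reservoir and conduit strain both remain comparable in AF. The investigator should record one as the main measure and treat the other as secondary, and should also state the role of PALS, which section 1.1 lists. Confirm that the software named in section 2.2.6 fits the chosen model.

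**Question and conclusion.** In the Study Summary (outline and Lay Summary), the Introduction, sections 1.1, 1.2, 2.3 and 4.1 and the project title in the Appendix, restate the aim as association with, and discrimination of, already diagnosed AF. Leave prediction of future AF as a hypothesis for a follow-up study. The monitoring and medication statements in sections 1.1, 2.3 and 4.1 must be reconciled with what the design can show.

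**Cost.** Nine places are reworded, together with the participant information sheet and lay summary where they repeat the claim, and any approval step that follows under section 4.2. The new model uses data already collected, since section 4.4 records age. The price is a more modest headline claim.

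**Alternative.** Keeping the prediction aim would mean following the sinus-rhythm groups for new AF, with a time-to-event model and an event-based sample size. At assumed rates of 0.5% to 5% a year, 156 people would yield about 0.8 to 7.6 events in one year and 3.9 to 34.5 in five. At 85% power and two-sided 0.05, an assumed hazard ratio per SD of 2.0 or 1.5 needs about 19 or 55 events. That is a different study from one due to finish in March 2024.

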#### 2.2.5 Power Calculation

The study aims to investigate significant differences in atrial strain values between subjects with atrial fibrillation (AF), hypertension (no AF), and healthy volunteers. To

achieve statistical power for this study, a large enough sample size must be obtained. This will be achieved via the use of power calculations utilising G\*Power 3.1 Statistical support has been provided and a sample size calculation was based on data found within the literature and involved detecting the smaller difference of left atrium contractile % between subjects with atrial fibrillation and healthy volunteers. The following criteria will be utilised: alpha level of 0.05, beta level of 15% and statistical power of 85%. Hence using this minimum value to determine our sample size (expected difference of 4.0, power = 0.85 and SD  $\pm$  7.5) and one-way ANOVA at three levels, a minimum sample size of at least 78 subjects in each group will be required for this study, total of 234 participants required. See Appendix Figures 1 & 2 for power calculation plots.

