# 4.4 Confidentiality

For patients that wish to participate in this study, all signed Informed Consent Forms will be securely stored in the Investigator Site File within the Cardio-Respiratory Department and must not leave the department under any circumstances. The participant data will undergo pseudo-anonymisation via the use of two password-protected excel spreadsheets. One spreadsheet will contain participant numbers and corresponding hospital ID numbers. The second spreadsheet will include participant numbers along with patient demographics (i.e., sex, age, participant group, reason for patient referral, etc.). This data will be encrypted and the folder it resides in will also be encrypted and password protected. This will be stored on an NHS OneDrive account on a departmental computer. General data protection regulation (GDPR) will be maintained and followed throughout.

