# **Appendix**

[1] -- Friday, January 20, 2023 -- 20:14:29 F tests - ANOVA: Fixed effects, omnibus, one-way A priori: Compute required sample size Analysis: Input: Effect size f 0.2177324 =  $\alpha$  err prob = 0.05 Power  $(1-\beta \text{ err prob})$ 0.85 = Number of groups = 3 Output: Noncentrality parameter  $\lambda$ = 11.0933311 Critical F = 3.0349206 Numerator df = 2 Denominator df = 231 Total sample size = 234

Actual power

Figure 1: Computed sample size of 234 utilising G\*Power 3.1. The following criteria was used: effect size of 0.25, alpha level of 0.05, beta level of 0.15 (15%), statistical power of 0.85 (85%) and a total of 3 groups – control, disease-control, and control.

=

0.8509156

Figure 2: Plotted total sample size over power utilising G\*Power 3.1, producing a sample size of 234 to achieve 85% significance. The following criteria was used: effect size of 0.25, alpha level of 0.05, beta level of 0.15 (15%), statistical power of 0.85 (85%) and a total of 3 groups – control, disease-control, and control.

Research Project: Can left atrial strain measurements, and correlating changes in left atrium area and volume size, be used as an early predictor of atrial fibrillation? [name]

				2022 2023														2024					
TASK DESCRIPTION	PLAN START	PLAN END	0	N	D	J	F	М	A	М	J	J	A	s	0	N	D	J	F	м	A	М	
Phase 1: Project Planning																							
Task 1: Project Proposal	24/10/2022	16/12/2022																					
Task 2: R&D Protocol	01/11/2022	30/11/2022																					
Task 3: Sponsorship Review Group Preparation	09/11/2022	13/02/2023																					
Task 4: Health Research Authority / NHS Research Ethics Service Approval	13/02/2023	01/05/2023																					
Task 5: Literature Review	01/02/2023	21/04/2023																					
Phase 2: Data Collection & Analysis																							
Task 1: Identify, Screen & Recruit Patients	01/06/2023	01/11/2023																					
Task 2: Conduct Echocardiograms	01/06/2023	01/11/2023																					
Task 3: Calculate LA Area & Volume	01/06/2023	01/11/2023																					
Task 4: Calulate Strain Analysis	01/06/2023	01/11/2023																					
Task 5: Conduct Data / Statistical Analysis	01/11/2023	01/01/2024																					
Phase 3: Dissertation																							
Task 1: Refine Literature Review	01/12/2023	01/01/2024																					
Task 2: Refine Methodology	01/12/2023	01/01/2024																					

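### Sex is recorded but enters no strain, area or volume comparison, so any sex imbalance between the diagnostic groups stays in the group differences

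*Combined protocol and SAP*

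**What the plan says.** The design is a single-centre, observational case-control study (2.2.1 and 2.2.2). Patients enter a group by diagnosis: normal sinus rhythm (NSR), NSR with controlled hypertension, or chronic AF. Age is the only matching variable named (2.2 Method; inclusion criterion 2).

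Sex is held in the study spreadsheet, which lists "patient demographics (i.e., sex, age, participant group, reason for patient referral, etc". Its only planned use is in 2.2.6: "For categorical data, such as gender, chisquared tests will be performed to determine any significant difference between groups". The section does not say what happens if the test is significant or if it is not.

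For strain, 2.2.6 plans "to compare the LA strain values between the control (NSR) and disease (AF) groups an independent T-test can be performed", then a one-way ANOVA across the three groups, and another across AF types. Mann-Whitney and Kruskal-Wallis tests replace these for non-normal data. The same methods are repeated for LA area and volume. Linear regression is planned only for the question of early prediction, and no covariates are named for it. No sex matching, stratification or covariate adjustment of the group comparisons appears in the protocol.

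**The concern.** Nothing in the design makes the proportion of men similar across groups recruited by diagnosis from echocardiogram referrals. If strain or LA size differs by sex, part of any group difference is a sex difference, and a one-factor test cannot separate the two. Section 1.1 says that the exclusions are meant to limit outside influences on strain and LA size. Sex is controlled by neither the exclusions, the matching nor the analysis.

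A test of imbalance does not fill the gap. It changes no estimate, and at this sample size a non-significant result says little about balance. At stake is how far the reported differences can be attributed to rhythm or hypertension, especially where the protocol itself expects small differences: the hypertensive group, expected to lie between the other two (section 1), and the AF types (2.3).

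**Working it through.** **Inputs from the documents.** From 2.2.5: "expected difference of 4.0, power = 0.85 and SD" 7.5, with "alpha level of 0.05, beta level of 15% and statistical power of 85"%, "one-way ANOVA at three levels", and 78 per group. From the Appendix output: "Effect size f 0.2177324".

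**Assumed inputs.** The documents give no sex mix by group and no effect of sex on strain. I take imbalances of 10 to 25 percentage points around 50% men, and a sex effect of 0 to 5 strain points. The 4.0 and the SD of 7.5 were set for contractile strain; I use them as the scale for strain in general.

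**1. The plan's own figure.** d = 4.0/7.5 = 0.5333. With the hypertension mean midway, f = d/√6 = 0.21773, as in the output. Then λ = 234 × 0.2177324² = 11.093, critical F(2, 231) = 3.0349, power = 0.851. The total of 234 reproduces. This pattern implies an NSR-hypertension gap of 4.0/2 = 2.0.

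**2. What the chi-squared test can show at 78 per group.** Two groups: λ = n(p₁ − p₂)² / [2p̄(1 − p̄)], 1 df, two-sided 5%.

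For 50% v 65%: 78 × 0.0225 / (2 × 0.575 × 0.425) = 3.59, power 47%.

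| Men, NSR v AF | λ | Power |
|---|---|---|
| 50% v 60% | 1.58 | 24% |
| 50% v 65% | 3.59 | 47% |
| 50% v 70% | 6.50 | 72% |
| 50% v 75% | 10.40 | 90% |

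The three-group test (2 df) depends on the pattern. For a 15-point spread, power is 38% with hypertension midway (50/57.5/65) and 48% if only one group differs (50/50/65). An observed 39/78 v 51/78, itself a 15-point imbalance, gives χ² = 3.78 and p = 0.052 without continuity correction.

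**3. Bias left in the unadjusted difference.** Bias = imbalance × sex effect. The standard error of a two-group difference is 7.5 × √(2/78) = 1.20. The error rate is the chance that a noncentral t on 154 df, with noncentrality bias/1.20, passes the two-sided 5% limits when there is no true group effect. At a 15-point imbalance:

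| Sex effect (points) | Bias | Share of 4.0 | Error rate |
|---|---|---|---|
| 0 | 0 | 0% | 5.0% |
| 1 | 0.15 | 4% | 5.2% |
| 2 | 0.30 | 8% | 5.7% |
| 3 | 0.45 | 11% | 6.6% |
| 4 | 0.60 | 15% | 7.9% |
| 5 | 0.75 | 19% | 9.5% |

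The bias can act in either direction. Against the 2.0 gap in step 1, 0.75 would be 0.75/2.0 = 38%, but only if the hypertension mean is midway.

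**4. Cost of adjusting for sex.** At 50% v 65%, the squared correlation of group with sex is (0.15²/4)/(0.575 × 0.425) = 0.023, so the variance inflation is 1/(1 − 0.023) = 1.02. By the normal approximation, two-group power for 4.0 falls from 91.5% to 90.9%, before any gain from variance that sex explains.

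**The case against.** The strongest reply is that the chi-squared test decides nothing, so its power cannot alter any strain estimate; the confounding would be the same at 10% or 99% power. That stands. A reader might infer that the plan uses the test as proof of balance, or that its low power causes the bias. Section 2.2.6 gives it no such role. The bias comes from the missing covariate, and the power figures show only that a non-significant result would not be reassuring.

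A reader might also pair the worst bias with a missed imbalance. A 25-point imbalance and a 4-point sex effect give a bias of 1.0 and an error rate of 13%, but the chi-squared test would flag that imbalance about 90% of the time. Where the test misses most, at 10 to 15 points, the bias is smaller. Flagging without adjustment still corrects nothing, yet 13% is not a fair headline.

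Three further points stand:

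- Both factors in the bias are assumed, and if sex has no effect on strain there is no bias.
- The error rate supposes no true NSR-AF difference, whereas the protocol expects one.
- 2.2.6 names no pairwise NSR-hypertension test, and section 1 places the hypertension mean only somewhere between the other two, so the share of a 2.0 gap is illustrative.

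The planned linear regression leaves its covariates unspecified rather than excluded. It serves the prediction question, however, and does not adjust the group comparisons. None of this supplies a way to deal with sex in those comparisons.

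**Conclusion.** The point holds in a limited form. In non-randomised groups matched on age alone, the plan records sex and leaves it out of every comparison of strain, LA area and LA volume. Any imbalance remains in those differences whatever the chi-squared result.

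Under the assumed 15-point imbalance and 0 to 5 point effect, the bias is 0 to 0.75 strain points, 0 to 19% of the planned 4.0, with an error rate of 5.0% to 9.5%. It might be inferred that sex could explain the NSR-AF difference; over this range it could not produce a difference of the planned size. The concern carries more weight for the hypertension and AF-subtype contrasts, because the same bias is a larger share of a smaller difference. The gap in the plan is certain; its size in this study is not known from the documents.

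**What to change.** In 2.2.6, pre-specify the following, to apply regardless of the chi-squared result:

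- For each strain measure that can be obtained in all the groups compared (reservoir, conduit, PALS), and for LA area and volume, fit a linear model on group, sex and age. Report adjusted mean differences with 95% CIs. Use the same form for the AF-type comparison.
- If residuals are clearly non-normal, keep the adjusted model and use a transformation or robust or bootstrap CIs, instead of dropping to unadjusted rank tests.
- Sections 1 and 1.1 say that contractile strain is absent in AF, so compare it, adjusted, only between groups in sinus rhythm.
- Report sex by group as description.

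The cost is a rewrite of the analysis text, somewhat more than one added sentence because the non-normal branch and the contractile phase need their own wording. Sex and age are already collected. The statistical price is two degrees of freedom and variance inflation of about 1.02 at a 15-point sex imbalance; no extra patients are needed on that account.
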